5.0 METHODOLOGY

5.1 Entry Criteria

5.1.1 Diagnosis/Condition for Entry into the Trial

The TNBC cohort will be comprised of patients with histologically confirmed locally advanced or metastatic TNBC that has relapsed on or is refractory to 1 or more lines of standard of care therapy. Patients must have received no more than one prior line of cytotoxic therapy for metastatic disease. Taxane and anthracycline-based chemotherapy must have been received, unless contraindicated. The NSCLC cohort will be comprised of male and female patients aged ≥ 18 years with histologically or cytologically confirmed metastatic NSCLC that is

immunotherapy naïve or previously treated with a maximum of 1 immunotherapy regimen AND chemotherapy naïve or previously treated with 1 cycle of platinum-containing chemotherapy. Patients will be screened for *EGFR* and *ALK* mutation. *EGFR/ALK* mutation-negative patients and patients with *EGFR* or *ALK* genomic tumor aberrations that have failed FDA-approved targeted therapy for these aberrations will be eligible for enrollment in the study. Written informed consent is required before performing any study-specific tests or procedures. Signing of the Informed Consent Form can occur outside the 28-day screening period. All screening evaluations must be completed and reviewed to confirm that patients meet all eligibility criteria before study entry. Results of standard-of-care tests or examinations performed prior to obtaining informed consent and within 28 days prior to study entry (except where otherwise specified) may be used for screening assessments rather than repeating such tests. The investigator will maintain a screening log to record details of all patients screened and to confirm eligibility or record reasons for screening failure, as applicable.

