Serum total bilirubin	≤1.0 X ULN (Subjects with known Gilbert's disease who have serum bilirubin level ≤3 X ULN may be enrolled)
Aspartate transaminase (AST) and Alanine transaminase (ALT)	≤2.5 X ULN with normal alkaline phosphatase (≤5 X ULN for subjects with liver metastases) OR ≤1.5 X ULN in conjunction with alkaline phosphatase >2.5 X ULN
Albumin	≥2.5 mg/dL
Coagulation	
International normalized ratio (INR) or prothrombin time (PT)	≤1.5 X ULN unless subject is receiving anticoagulant therapy as long as PT or aPTT is within therapeutic range of intended use of anticoagulants
Activated partial thromboplastin time (aPTT)	≤1.5 X ULN unless subject is receiving anticoagulant therapy as long as PT or aPTT is within therapeutic range of intended use of anticoagulants
^a CrCl should be calculated per institutional standard.	

8. Life expectancy ≥ 6 months.
9. ≥ 4 weeks since any major surgery.
10. A 2-week washout period post any prior systemic anticancer therapy, RT, targeted anticancer therapy or mAb, and/or investigational therapy is required prior to trial entry. Subject should be recovered (i.e., ≤ Grade 1 or at baseline) from AEs due to a previously administered therapy.
 - Note: Subjects with ≤ Grade 2 neuropathy are an exception to this criterion and may qualify for the study.
11. Female subjects of childbearing potential should have a negative serum pregnancy (β-human chorionic gonadotropin [β-HCG]) within 7 days prior to receiving the first dose of the trial treatment and should not be lactating.
12. Female subjects of childbearing potential (Section 5.5.2) must be willing to use an adequate method of contraception as outlined in Section 5.5.2 – Contraception, for the course of the study through 120 days after the last dose of study medication.

Note: Abstinence is acceptable if this is the usual lifestyle and preferred contraception for the subject.
13. Male subjects of childbearing potential (Section 5.5.2) must agree to use an adequate method of contraception as outlined in Section 5.5.2 – Contraception, starting with the first dose of study therapy through 120 days after the last dose of study therapy.

Note: Abstinence is acceptable if this is the usual lifestyle and preferred contraception for the subject.

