5.1.3 Subject Exclusion Criteria

Subjects meeting any of the following exclusion criteria must be excluded from participating in the trial:

1. Unwilling or unable to comply with the study protocol.
2. Subjects for who bone metastases are the only available non-target lesions for abscopal effect evaluation.
3. Subjects with tumors for which SBRT is not considered appropriate standard therapy with the exception of subjects with a primary breast tumor. This includes subjects with target lesions less than 1 cm in diameter and those with large central lung lesions.
4. Diagnosis of immunodeficiency or is receiving systemic steroid therapy or any other form of immunosuppressive therapy within 7 days prior to the first dose of trial treatment.
5. Known history of active tuberculosis (Bacillus Tuberculosis).
6. Known or suspected hypersensitivity to pembrolizumab or any of its excipients or any component of the proposed regimen (gene vector/valacyclovir).
7. Known gallbladder or bile duct disease (i.e., infection or cholecystitis) or acute or chronic pancreatitis.
8. ECOG performance status of ≥ 2 or oxygen dependence (e.g., advanced chronic obstructive pulmonary disease).
9. Inability to swallow food or any condition of the upper gastrointestinal tract that precludes administration of oral medications (valacyclovir).
10. Congestive heart failure: New York Association class III or IV heart failure or unstable angina (see Section 12.4).
11. Sustained or clinically significant cardiac arrhythmias including sustained ventricular tachycardia, ventricular fibrillation, clinically significant bradycardia, advanced heart block (Mobitz II or higher atrioventricular nodal block), prolonged corrected QT interval (longer than 470 milliseconds), or history of acute myocardial infarction.
12. Concomitant disease(s) that could prolong QT such as autonomic neuropathy (caused by diabetes or Parkinson's disease), human immunodeficiency virus (HIV), cirrhosis, uncontrolled hypothyroidism, or cardiac failure.
13. History of syncope or family history of idiopathic sudden death.
14. Known additional malignancy that is progressing or requires active treatment. Exceptions include basal cell carcinoma of the skin or squamous cell carcinoma of the skin that has undergone potentially curative therapy or in situ cervical cancer.

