6.0 TRIAL FLOW CHART

6.1 Trial Flow Chart

Visit	Screening ^a	Baseline ^b	V1	V2	V3	V4	V5	V6	V7	V8	V9	V10*	EOT	
Day	-28 to -1	-7 to -1	0±5	2±5	4±5	7±5	9±5	11±5	17±5	38±5	59±5	80*±5		
Informed Consent	X													
Inclusion/ Exclusion	X													
Demographics	X													
Medical History	X													
Physical Exam ^c	X		X						X	X	X	X	X	
Height	X													
Weight	X		X						X	X	X	X	X	
ECOG Performance Status	X		X						X	X	X	X	X	
12-Lead ECG and MUGA Scan or Echocardiogram ^d	X												X	
Concomitant Therapies	Continuous from screening period													
Hematology ^e	X		X						X	X	X	X	X	
Clinical Chemistry ^e	X		X						X	X	X	X	X	
Urinalysis ^f	X													
Serum Pregnancy (β-hCG) ^g	X													
Tumor Assessments (modified irRC and RECIST 1:1) ^h	X												X	
Brain MRI (NSCLC patients only) ⁱ	X													
Biopsy ^j			X						X					
Correlative Studies Blood Collection ^k	X								X		X			
AEs and SAEs	From informed consent signing up to 30 days after the last treatment dose^m													
ADV/HSV-tk Administration ^l			X											
Valacyclovir Administration ^l			X											
SBRT Administration ^l				X	X	X	X	X						
Pembrolizumab Administration ^l									X	X	X	X		

Abbreviations: AE = adverse event; ALT = alanine transaminase; ANC = absolute neutrophil count; aPTT = activated partial thromboplastin time; AST = aspartate transaminase; β -hCG, beta-human chorionic gonadotropin; BUN = blood urea nitrogen; CBC = complete blood count; CT = computed tomography; ECG = electrocardiogram; ECOG = Eastern Cooperative Oncology Group; EOT = end of treatment; GM-CSF = granulocyte macrophage colony-stimulating factor; IFN = interferon; IL = interleukin; INR = international normalized ratio; LDH = lactate dehydrogenase; MRI = magnetic resonance imaging; MUGA = multigated acquisition; Q3W = every 3 weeks; PD-1 = programmed death-1; PD-L1 = programmed death-ligand 1; PET = positron emission tomography; p.o. = orally; PT = prothrombin; RT = radiation therapy; SAE = serious adverse event; T3 = triiodothyronine; T4 = thyroxine; Th1 = T-helper; t.i.d. = three times daily; TIL = tumor-infiltrating lymphocyte; TNF = tumor necrosis factor; TSH = thyroid-stimulating hormone; vp = viral particles; WBC = white blood cell. A window of ± 5 days is allowed for visits and study assessments (except as otherwise specified).

a. Within 28 days prior to Day 0 of ADV/HSV-tk.

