b. Within 7 days prior to Day 0 of ADV/HSV-tk. Only screening procedures not performed within 7 days of ADV/HSV-tk dosing are required at baseline.

c. The baseline symptom-medical history and physical examination are not required if the screening medical history and physical examination were conducted within 7 to 28 days prior to Day 0 of ADV/HSV-tk. Vital sign (blood pressure, respiratory rate, pulse, and oral temperature) measurements will be performed at each physical exam.

d. A 12-lead ECG will be performed at screening, at EOT, and when clinically indicated. MUGA scan or echocardiogram will be performed only if clinically indicated.

e. A blood sample for CBC with platelet count and differential WBC count will be obtained at screening, on Days 0 and 17, every 3 weeks thereafter until completion of the protocol-specified treatment, at EOT, and when clinically indicated.

If a patient is found to have an ANC $< 1.5 \times 10^9/L$, platelet count $< 100 \times 10^9/L$, or both, the CBC with differential should be repeated at least every other day until the ANC and platelet count have exceeded these values.

A blood sample for clinical chemistry panel (albumin, glucose, sodium, potassium, carbon dioxide, chloride, calcium, BUN, creatinine, total bilirubin, total protein, alkaline phosphatase, AST, and ALT) and evaluation of phosphorus, magnesium, and LDH will be obtained at screening, on Days 0 and 17, every 3 weeks thereafter until completion of the protocol-specified treatment, at EOT, and when clinically indicated. PT/INR and aPTT will be tested at screening and on Day 17. TSH, free T4, and total T3 will be tested at screening and when clinically indicated.

f. Urinalysis (blood, glucose, protein, specific gravity) will be performed at screening and when clinically indicated.

g. For women of childbearing potential, the results of a serum β -hCG pregnancy test must be negative within 7 days before the first treatment dose is administered. If the screening serum β -hCG pregnancy test is performed more than 7 days before ADV/HSV-tk dosing, it must be repeated at baseline, with results known to be negative prior to the first dose of the study treatment. Testing is to be repeated as clinically indicated.

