h. For tumor assessments, CT scan of the chest, abdomen, and pelvis will be performed at screening, every 8 weeks thereafter and/or at the discretion of the treating physician, when clinically indicated, and 30 days after the last dose of pembrolizumab. For patients with equivocal CT scan results, PET scan will be performed. For abscopal effect evaluation, CT-based response assessment of non-target lesions will be performed at screening, every 8 weeks thereafter, and 30 days after the last dose of pembrolizumab.

i. Brain MRI will be performed on NSCLC patients only at screening.

j. In patients with accessible tumor, biopsies will be conducted at Day 0 and 3 (± 2) days after the first dose of pembrolizumab. Patients whose disease progresses while on treatment will also undergo biopsy before they start their new treatment. Banked tumor tissue obtained as part of the patient's standard care and additional biopsy tissues will be evaluated for correlative biomarkers including cytokine expression (IL-1, IL-2, IL-6, IL-12, IFN-c, TNF- α , and GM-CSF), TILs, PD-1 and PD-L1 expression, and mutation load. Cytokine expression, TILs, and PD-1 and PD-L1 expression will also be analyzed for abscopal effect evaluation.

k. Blood samples for correlative studies will be collected at screening, 3 (± 2) days after the first dose of pembrolizumab, and end of Cycle 2 of pembrolizumab. An additional sample will be collected from patients whose disease progresses while on treatment. Blood will be collected into standard vacutainer tubes (3 green top tubes).

l. ADV/HSV-tk (5×10^{11} vp) in a 2-mL total volume will be injected intratumorally (single-site injection) on Day 0 of the study. The study coordinator will dispense the 14-day quantity of valacyclovir to the patient on Day 0. The patient will be instructed to take valacyclovir (2 g) p.o. t.i.d. for 14 days (from Day 1 to Day 15 of the study). Primary lung tumors and metastatic lesions (breast and lung) will be treated with SBRT of 30 Gy (6 Gy X 5 fractions). Primary breast

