7.1.2.8 Tumor Tissue and Blood Collection and Correlative Studies

In patients with accessible tumor, biopsies will be conducted at Day 0 and 3 (\pm 2) days after the first dose of pembrolizumab. Subjects whose disease progresses while on treatment will undergo an additional biopsy before starting their new treatment. Banked tumor tissue obtained as part of the subject's standard of care and collected biopsy tissues will be evaluated for Th1 response by cytokine expression (IL-1, IL-2, IL-6, IL-12, IFN- γ , TNF- α , and GM-CSF); TILs; PD-1 and PD-L1 expression; and mutation load. PD-1 and PD-L1 expression, immune infiltrates, and cytokine expression will also be analyzed for abscopal effect evaluation.

Blood samples for correlative studies will be collected at screening, 3 (\pm 2) days after the first dose of pembrolizumab, and end of Cycle 2 of pembrolizumab. An additional sample will be collected from subjects whose disease progresses while on treatment. Blood samples will be collected into standard vacutainer tubes (2 green top tubes). Samples will be evaluated for profile of circulating suppressor and effector immunocytes and cytokines.

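### The only scheduled pre-treatment correlative blood sample is a screening draw that is tied to neither the anticancer nor the steroid washout; a Day 0 pre-injection draw would be a cleaner exploratory baseline

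*Combined protocol and SAP*

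**What the plan says.** Section 6.1, footnote k, and section 7.1.2.8 give the same schedule for correlative blood: "Blood samples for correlative studies will be collected at screening", then 3 (±2) days after the first pembrolizumab dose, then at the end of Cycle 2, with a further sample at progression on treatment. The flow chart row is marked at Screening, V7 and V9, with nothing at Baseline or Day 0. Footnote a defines screening as "Within 28 days prior to Day 0 of ADV/HSV-tk".

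The two washout rules have other anchors. Criterion 10 of section 5.1.2 reads: "A 2-week washout period post any prior systemic anticancer therapy, RT, targeted anticancer therapy or mAb, and/or investigational therapy is required prior to trial entry". Section 5.1.3, criterion 4, excludes a patient who "is receiving systemic steroid therapy or any other form of immunosuppressive therapy within 7 days prior to the first dose of trial treatment". Section 5.1.1 puts screening ahead of entry: "All screening evaluations must be completed and reviewed to confirm that patients meet all eligibility criteria before study entry".

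Footnote b adds a general rule for the Baseline column (Day -7 to -1): "Only screening procedures not performed within 7 days of ADV/HSV-tk dosing are required at baseline". The tissue baseline is set differently. In patients with accessible tumor, "biopsies will be conducted at Day 0" (section 7.1.2.8).

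**The concern.** The samples profile circulating suppressor and effector immunocytes and cytokines. They serve the exploratory objectives in section 3.3, one of which is to measure the immune response to the regimen. Section 1.0 lists no control, so change from the pre-treatment sample is the natural within-patient evidence.

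A patient can give that sample while still on prior therapy or steroids, or within days of stopping them, and still be eligible. Any recovery of the markers between the draw and the first on-treatment sample is then mixed with the effect of the regimen. Every TNBC patient (28 of the planned 57) has had at least one prior line under section 5.1.1, although how recently will vary. Section 5.1.3, criterion 15, also admits patients with treated, stable brain metastases who have been off steroids for 7 days, so recent steroid use is foreseen. A badly timed baseline sample cannot be retaken once treatment has started.

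**Working it through.** The plan gives no figure for the correlative blood, so there is nothing to reproduce. The check is day arithmetic on the stated windows.

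**Inputs.** Screening is Day -28 to -1 (footnote a). Baseline is Day -7 to -1 (footnote b). First pembrolizumab is Day 17 ±1 (footnote l), and the first on-treatment sample is 3 ±2 days later (footnote k). The washouts are 14 days before trial entry (5.1.2) and 7 days before first dose (5.1.3). Assumptions: Day 0 is the day of injection and the first dose; trial entry is Day 0 (varied in step 4); the latest permitted anticancer therapy is then Day -14 and the latest permitted steroid Day -7. The specific ±1 day in footnote l is used rather than the general ±5-day visit window.

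**Step 1: first on-treatment sample.** Earliest (17 - 1) + (3 - 2) = Day 17. Latest (17 + 1) + (3 + 2) = Day 23.

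**Step 2: gap from the baseline draw to that sample.**
- Screening draw: 17 - (-1) = 18 to 23 - (-28) = 51 days.
- Footnote b draw: 17 - (-1) = 18 to 23 - (-7) = 30 days.
- Day 0 draw: 17 to 23 days.

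**Step 3: days from latest permitted exposure to the draw (draw day minus exposure day).**

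| Draw | After anticancer therapy on Day -14 | After steroid on Day -7 |
|---|---|---|
| Screening, Day -28 to -1 | -14 to 13 | -21 to 6 |
| Footnote b, Day -7 to -1 | 7 to 13 | 0 to 6 |
| Day 0, before injection | 14 | 7 |

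Negative values mean that the draw comes before the last exposure. Of the 28 screening days, 14 (Day -28 to -15) precede the latest permitted anticancer therapy and 21 (Day -28 to -8) precede the latest permitted steroid. No screening day, and no footnote b day, guarantees a full 14 or 7 days.

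**Step 4: earlier trial entry.** With entry on Day -E, the latest permitted anticancer therapy is Day -(E + 14), so 14 days are guaranteed only for draws on or after Day -E. Entry on Day -1, -7 or -14 gives 1, 7 or 14 of the 28 screening days, and 1, 7 or 7 of the 7 footnote b days. The steroid column does not change, because that limit is counted from first dose. A Day 0 draw still gives at least 14 and 7 days.

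**Step 5: does footnote b reach correlative blood?** Read literally it does, because the draw is a procedure marked under Screening. Against that, the pregnancy test has its own instruction in footnote g ("it must be repeated at baseline, with results known to be negative prior to the first dose of the study treatment"), while footnote k has none. Footnote c exempts history and physical examination done 7 to 28 days before Day 0. The empty Baseline column settles nothing, since no row has a mark there. The text does not resolve the question.

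**The case against.** The strongest reply is footnote b. If it covers correlative blood, the sample is at most 7 days old at Day 0, the longest gap falls from 51 to 30 days, and blood and tissue baselines are at most 7 rather than 28 days apart. If trial entry is also on or before Day -7, the anticancer washout is complete at every such draw. This stands as far as it goes. It depends on a reading that footnote k does not confirm, and it leaves the steroid interval at 0 to 6 days.

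Other replies also stand:
- Step 3 uses the shortest permitted washout. The share of patients near that limit cannot be derived, and chemotherapy-naïve NSCLC patients are eligible.
- Entry requires minimum blood counts and recovery of adverse events to Grade 1 or baseline, although neither is a measure of the immune markers.
- Medications in the 28 days before first dose are recorded (5.3.1) and prior cancer treatments are reviewed (7.1.1.5.2), so recent exposure can be examined.
- A Day 0 draw guarantees only 14 and 7 days, and recovery could continue after that.

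A reader might infer that recovery will show up as a treatment effect, or that the bias favors the regimen. The documents do not support either. They give no size or direction for any rebound, and the panel includes both suppressor and effector cells. Nor do they say that each biomarker change is measured from this sample: section 8.1 specifies no correlative analysis.

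**Conclusion.** The point holds as a limited design weakness. The schedule does not require either washout to be complete when the only planned pre-treatment correlative sample is drawn. This remains true if footnote b applies and trial entry is Day 0 (7 to 13 days after anticancer therapy, 0 to 6 after steroids). If entry is on or before Day -7 and footnote b applies, only the steroid part remains.

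Confounding of recovery with immune response is therefore possible in patients with recent therapy or steroids; its size, direction and frequency are unknown. The effect is confined to exploratory blood markers. ORR does not use this sample, and the tissue markers have a Day 0 biopsy. Low priority: a cheap improvement.

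**What to change.** In footnote k, the flow chart row and section 7.1.2.8, move the baseline correlative draw from screening to Day 0 (V1), before the ADV/HSV-tk injection, with the hematology and chemistry draw and the biopsy already planned that day. State that this sample is the baseline for blood biomarker changes. This also removes the doubt about footnote b.

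Because a Day 0 draw reduces the confounding without removing it, use the prior-treatment and medication records to describe time since last anticancer therapy and last steroid alongside the biomarker results. Confirm that the case report form captures those stop dates.

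The cost is small. The number of samples is unchanged, and blood is already taken at that visit. The one downside is a further research draw to complete before injection on Day 0.

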7.0 TRIAL PROCEDURES

7.1 Trial Procedures

The Trial Flow Chart - Section 6.0 summarizes the trial procedures to be performed at each visit. Individual trial procedures are described in detail below. It may be necessary to perform these procedures at unscheduled time points if deemed clinically necessary by the investigator.

Furthermore, additional evaluations/testing may be deemed necessary by the Sponsor and/or Merck for reasons related to subject safety. In some cases, such evaluation/testing may be potentially sensitive in nature (e.g., HIV, hepatitis C, etc.) and thus, local regulations may require that additional informed consent be obtained from the subject. In these cases, such evaluations/testing will be performed in accordance with those regulations.

7.1.1 Administrative Procedures

7.1.1.1 Informed Consent

The investigator must obtain documented consent from each potential subject prior to participating in a clinical trial.

Consent must be documented by the subject's dated signature or by the subject's legally acceptable representative's dated signature on a consent form along with the dated signature of the person conducting the consent discussion.

A copy of the signed and dated consent form should be given to the subject before participation in the trial.

The initial informed consent form, any subsequent revised written informed consent form, and any written information provided to the subject must receive the IRB/ERC's approval/favorable opinion in advance of use. The subject or his/her legally acceptable representative should be informed in a timely manner if new information becomes available that may be relevant to the subject's willingness to continue participation in the trial. The communication of this information will be provided and documented via a revised consent form or addendum to the original consent form that captures the subject's dated signature or by the subject's legally acceptable representative's dated signature.

Specifics about a trial and the trial population will be added to the consent form template at the protocol level.

The informed consent will adhere to IRB/ERC requirements, applicable laws and regulations, and Sponsor requirements.

